# 3.3.5 Chronic Rhinosinusitis History

The following baseline disease characteristics for chronic rhinosinusitis will be summarized by treatment group and in total for the Safety Analysis Set as well as for the Efficacy Analysis Set in Part 2:

- Time from diagnosis of CRS (years)
  - Time from diagnosis of CRS (years) is calculated as (date of informed consent –
    date of diagnosis + 1)/365.25 if the dates are full; (month difference of date of
    informed consent and date of diagnosis)/12 if only day is missing; year difference
    of date of informed consent and date of diagnosis if both month and day are
    missing.
- Asthma status (yes or no)
- Perennial Allergic Rhinitis (yes or no or unknown)
- Seasonal Allergic Rhinitis (yes or no or unknown)
- Chronic Obstructive Pulmonary Disease (COPD) (yes or no)
- Smoking History (never, current, and former)
- Sensitive to nonsteroidal anti-inflammatory drugs (yes or no)
- Current or history of medication related to CRS:
  - Intranasal corticosteroid spray
  - Oral corticosteroids
  - Antibiotics
  - Saline irrigation
  - o Other medication

## 3.3.6 Chronic Rhinosinusitis Surgical History

The following baseline disease characteristics for chronic rhinosinusitis surgery will be summarized by treatment group and in total for the Safety Analysis Set as well as for the Efficacy Analysis Set in Part 2:

- Complete bilateral ethmoidectomy (yes or no)
- Nasal Polyps (yes or no)
- Septoplasty (yes or no)
- Nasal surgery involving turbinates (yes or no)

- Sinuplasty (yes or no)
- Polypectomy (yes or no)
- Facial Trauma (yes or no)

#### 3.3.7 Medical History

Medical history (non-chronic rhinosinusitis medical/surgical history) will be coded using the Medical Dictionary for Regulatory Activities (MedDRA) version 24.1 (or later version). Counts and percentages of subjects with medical history by primary system organ class and preferred term will be summarized by treatment and in total for the Safety Analysis Set as well as for the Efficacy Analysis Set in Part 2.

#### 3.3.8 Prior and Concomitant Medications

Prior and concomitant medications will be coded to anatomical therapeutic chemical (ATC) class and preferred name using the WHODrug Dictionary version B3 Global, Sep2021 (or later version). For summary purposes, medications will be considered prior medications if they were stopped prior to study treatment administration and concomitant medications if they were after treatment administration but no later than 31 days (>31 days) after discontinuation of study treatment. Medications stopping on the same day as study treatment administration will be considered as concomitant medications.

If a medication has incomplete start or stop dates, dates will be imputed to determine whether a medication should be considered prior medication or concomitant medication based on the rules in Section 3.1.10.1

Counts and percentages of subjects taking prior and concomitant medications by ATC class and preferred name will be summarized by treatment and in total for the Safety Analysis Set as well as for the Efficacy Analysis Set in Part 2.

Incomplete start and stop dates will be listed as collected without imputation.

3.3.9 Study Drug Exposure (Up to Matrices Removal or Dislodgement) and Compliance

Days of exposure to study drug will be calculated from the date of study treatment (LYR-220 or sham) administration. Days of exposure to study drug will be summarized by treatment and in total for the Safety Analysis Set as well as for the Efficacy Analysis Set in Part 2 with descriptive statistics and with counts and percentages of subjects with exposure in the following categories:

- <2 weeks (1 14 days)

- 2 <4 weeks (15 28 days)

- 4 <8 weeks (29 56 days)

- 8 <12 weeks (57 84 days)

- 12 <16 weeks (85 112 days)

- 16 <20 weeks (113 140 days)

- 20 <24 weeks (141 168 days)

- 24 <25 weeks (169 175 days)

- 25 <26 weeks (176 182 days)

- ≥26 weeks (≥183 days)

Compliance to the study drug regimen will not be calculated.

The LYR-220 administration/Sham procedure will be summarized by treatment and in total for the Safety Analysis Set as well as for the Efficacy Analysis Set in Part 2 for the following items:

- Pre-procedure endoscopy performed
- · Topical anesthesia applied before imaging
- Topical decongestant sprays applied before imaging
- Pre-procedure endoscopy assessments
  - o Septal deviation
  - Nasal polyps
  - o Concha bullosa
  - o Other

# 3.4 Efficacy Assessment

Efficacy data will be summarized by treatment for each part based on the Efficacy Analysis Set.

For Part 1, efficacy data will be summarized descriptively by arms (LYR-220-16 and LYR-220-32) without formal statistical test.

For Part 2, hypothesis testing for efficacy endpoints will be conducted comparing LYR-220-32 to sham on the Efficacy Analysis Set with 1-sided testing and present a 2-sided 90% CI. For subjects with polyp status is different from the IRT and eCRF, the polyp status that is recorded on Day 1 before the insertion procedure in the eCRF will be used.

Efficacy data will be listed by site and subject.

3.4.1 Primary Efficacy Endpoint

Not applicable. Efficacy analyses are considered secondary for this study.

- 3.4.2 Secondary Efficacy Endpoints
- 3.4.2.1 CFBL in SNOT-22 Total and Subdomain Scores at Weeks 2, 4, 6, 8, 12, 16, 20, 24, and 28/Follow Up
- 3.4.2.1.1 Definition of Estimand for Part 2

The key attributes of the estimand are as following (ICH E9(R1) (FDA 2021))1:

Treatment LYR-220 7500 µg drug matrix over a 24-week period or sham procedure

Population subjects with CRS who have had prior bilateral ethmoidectomy meeting the defined inclusion/exclusion criteria

Variable CFBL in SNOT-22 total and subdomain scores at Weeks 2, 4, 6, 8, 12, 16, 20, 24, and 28/Follow Up

Population-level summary mean change from baseline of the difference between LYR-220-32 and sham

Analysis model MMRM model will include the fixed, categorical effects of treatment, visit, treatment-by-visit interaction, and nasal polyp stratum as well as the continuous, fixed covariates of baseline score and baseline score-by-visit interaction. The ANCOVA model will include treatment, nasal polyp stratum as fixed-effect terms and baseline score as a covariate.

## Intercurrent events (ICE) and strategy

- (1) ICE1: Rescue treatment: efficacy data collected after rescue treatment will not be used (Hypothetical Strategy)
- (2) ICE2: Premature treatment discontinuation: efficacy data collected after treatment discontinuation will be included in the analysis regardless of attribution to treatment (Treatment Policy Strategy)

If both ICE1 and ICE2 occur for the same subject, addressing ICE1 takes precedence over ICE2. For example, if a subject took rescue medication at Week 10, and subsequently dropped out at Week 12 with no score at Week 24, then the method addressing ICE1 will be used.

3.4.2.1.2 Statistical Analysis for CFBL in SNOT-22 Total and Subdomain Scores 3.4.2.1.2.1 Part 1

Descriptive summary statistics on the values and changes from baseline will be presented for the SNOT-22 total and subdomain score at each analysis visit by treatment group.

3.4.2.1.2.2 Part 2

Statistical analysis of the CFBL in SNOT-22 total and subdomain scores at Weeks 2, 4, 6, 8, 12, 16, 20, 24, and 28/Follow-up will be carried out based on the Efficacy Analysis Set.

MMRM model without imputation: analysis will be carried out using MMRM model with the CFBL in SNOT-22 score as the dependent variable, and include the fixed, categorical effects of treatment, visit, treatment-by-visit interaction, and nasal polyp stratum as well as the continuous, fixed covariates of baseline score and baseline scoreby-visit interaction. An unstructured covariance structure shared across treatment groups will be used to model the within-subject errors. The covariance parameters in the above model will be fitted through a working model that assumes joint multivariate normality (MVN) of responses by maximizing the restricted likelihood (REML) under the working model, and the mean parameters will be estimated by generalized least squares after plugging in REML estimate of covariance parameters. In case the model does not converge with the unstructured covariance structure, the heterogenous Toeplitz structure (TOEPH) will be used instead. In case the model will not converge with the TOEPH structure, heterogenous compound symmetry (CSH) will be used instead. The Kenward-Roger approximation will be used to estimate denominator degrees of freedom and adjust nominal standard errors based on the inverse observed information from the working MVN model. Missing data will be handled by the MMRM under the missing at random (MAR) assumption.

Least-squares means (LS-means) for change from baseline at each analysis visit will be provided for each treatment group and the difference between LYR-220 and sham treatment at each analysis visit will be estimated from the MMRM model.

Descriptive summary statistics on the values and changes from baseline will be presented for the SNOT-22 total and subdomain score at each analysis visit by treatment group.

Graphic displays of the results will be presented. The by-visit means and the standard errors for each treatment will be plotted against the analysis visit. In addition, the by-visit least squares mean changes and the standard errors for each treatment will also be plotted against the analysis visit.

- MMRM model with subject's worst score imputation: analysis will be carried out in the same manner as MMRM model without imputation except that post-rescue assessments will be imputed with subject's worst score from baseline (including baseline) through Week 28/Follow Up. Other missing data will be handled by MMRM model.
- Analysis of covariance (ANCOVA) with multiple imputation: an ANCOVA model will be performed to compare mean change from baseline in the SNOT-22 total and subdomain scores at Week 24 and Week 28/Follow-up between the LYR-220 and the sham treatment. Post-rescue Week 24 and Week 28/Follow-up assessments will be imputed with subject's worst score from baseline (including baseline) through Week 28/Follow Up. The ANCOVA model will include treatment, nasal polyp stratum as fixed-effect terms and baseline score as a covariate. The least-squares (LS) mean change for each treatment group, the LS mean difference between treatment groups will be reported. Missing data will be imputed with a multiple imputation procedure under the assumption of MAR. The imputation model will include nasal polyp stratum, baseline score and post baseline scores to impute the missing SNOT-22 score with monotone regression method and MCMC method will be used to produce monotone missing pattern. In case the imputation model does not converge, the model will be reduced to include nasal polyp stratum, baseline score, partial or no post baseline scores. There will be 50 imputed datasets derived using SAS PROC MI based on the pre-specified model above with a given random seed (protocol date). The ANCOVA model will be performed on each dataset after imputing the missing scores and PROC MIANALYZE will be used to combine the results.
- Analysis of covariance (ANCOVA) with last observation carried forward (LOCF) imputation: an ANCOVA model will be carried out in the same manner as ANCOVA model with multiple imputation. Post-rescue Week 24 and Week 28/Follow-up assessments will be imputed with subject's worst score from baseline (including baseline) through Week 28/Follow Up. Other missing data at Week 24 and Week 28/Follow-up will be imputed with the last value observed before missingness.

Descriptive summary statistics on the values and changes from baseline will be presented for the above secondary efficacy endpoints at each analysis visit by treatment group. In addition, reduction in SNOT-22 total score will be descriptively summarized for the following aspects:

Percentage of subjects with total score < 20 at Week 24,

- Percentage of subjects with a minimal clinically important difference (MCID) = 9
   reduction from baseline at each timepoint,
- Percentage of subjects with a ≥ 50% reduction from baseline at each timepoint,
- Percentage of subjects with a ≥ 75% reduction from baseline at each timepoint.
- 3.4.2.2 CFBL in Cardinal Symptom Scores, Loss of Smell Score at Weeks 2, 4, 6, 8, 12, 16, 20, 24, and 28/Follow-up

## 3.4.2.2.1 Part 1

Descriptive summary statistics on the values and changes from baseline will be presented at each analysis visit by treatment group.

#### 3.4.2.2.2 Part 2

The estimands attributes for the following secondary efficacy endpoints are defined in the same manner as for "CFBL in SNOT-22 Total and Subdomain Scores" in Section 3.4.2.1.1:

- CFBL in the composite and individual cardinal symptom score at Weeks 2, 4, 6, 8, 12, 16, 20, 24, and 28/Follow Up;
- CFBL in loss of smell score at Weeks 2, 4, 6, 8, 12, 16, 20, 24, and 28/Follow-up for subjects with baseline score ≥ 2.

The same analysis methods used for the SNOT-22 total and subdomain scores will be used for the above secondary efficacy endpoints. The LS-means for change from baseline at each analysis visit will be provided for each treatment group and the difference between LYR-220 and sham treatment at each analysis visit will be estimated along with the Cls. The p-value for the comparison at each analysis visit will also be presented.

Descriptive summary statistics on the values and changes from baseline will be presented for the above secondary efficacy endpoints at each analysis visit by treatment group.

3.4.2.3 CFBL in CRS-PRO at Weeks 2, 3, 4, 6, 8, 12, 16, 20, 24, and 28/Follow-up 3.4.2.3.1 Part 1

Descriptive summary statistics on the values and changes from baseline will be presented at each analysis visit by treatment group.

# 3.4.2.3.2 Part 2

CRS-PRO subdomain scores will be summarized descriptively without formal statistical test.

Descriptive summary statistics on the values and changes from baseline will be presented for CRS-PRO total and subdomain scores at each analysis visit by treatment group.

The estimands attributes for CRS-PRO are defined in the same manner as for "CFBL in SNOT-22 Total and Subdomain Scores" in Section 3.4.2.1.1. Missing data will not be imputed. The same MMRM analysis method used for the SNOT-22 total and subdomain scores will be used for CRS-PRO total score. The LS-means for change from baseline at each analysis visit will be provided for each treatment group and the difference between LYR-220 and sham treatment at each analysis visit will be estimated along with the CIs. The p-value for the comparison at each analysis visit will also be presented.

## 3.4.2.4 CFBL in PGIS at Weeks 8, 16, and 24

#### 3.4.2.4.1 Part 1

Descriptive summary statistics on the values and changes from baseline will be presented at each analysis visit by treatment group.

#### 3.4.2.4.2 Part 2

The estimands attributes are defined in the same manner as for "CFBL in SNOT-22 Total and Subdomain Scores" in Section 3.4.2.1.1. Missing data will not be imputed. The same MMRM analysis method used for the SNOT-22 total and subdomain scores will be used. The LS-means for change from baseline at each analysis visit will be provided for each treatment group and the difference between LYR-220 and sham treatment at each analysis visit will be estimated along with the CIs. The p-value for the comparison at each analysis visit will also be presented.

Descriptive summary statistics on the values and changes from baseline will be presented for the above secondary efficacy endpoints at each analysis visit by treatment group.

3.4.2.5 Time-to-First Recommendation of Rescue Treatment through Week 28/Follow-up 3.4.2.5.1 Part 1

Time to first recommendation of rescue treatment will be analyzed using Kaplan-Meier (K-M) method. The K-M estimate of median time to first recommendation of rescue treatment with CI (if estimable) will be presented for each treatment group. K-M estimates of quartiles (25th and 75th percentiles) will also be presented for each treatment group.

#### 3.4.2.5.2 Part 2

Time to first recommendation of rescue treatment will be analyzed using Kaplan-Meier (K-M) method. The K-M estimate of median time to first recommendation of rescue treatment with CI (if estimable) will be presented for each treatment group. Estimates of quartiles (25th and 75th percentiles) will also be presented for each treatment group. Time to first recommendation of rescue treatment will be compared between LYR-220 group and the sham procedure group using the log-rank test stratified by the stratification factor. P-value from the log-rank test will be presented.

K-M estimates of the survival function for time to first recommendation of rescue treatment will be graphically displayed for each treatment group.

3.4.2.6 Systemic/Oral Corticosteroid Use or Sinonasal Surgery Recommendation through Week 28/Follow-up

#### 3.4.2.6.1 Part 1

The endpoint will be summarized using the number and percentage of subjects being recommend by treating physician for systemic/oral steroid use or sinonasal surgery in each treatment group.

#### 3.4.2.6.2 Part 2

The endpoint will be summarized using the number and percentage of subjects being recommended by treating physician for systemic/oral corticosteroid use or sinonasal surgery in each treatment group. Comparison between LYR-220 group and the sham procedure group will

be performed using a Cochran-Mantel-Haenszel (CMH) test controlling for nasal polyp status. The general association p-value will be provided. The odds ratio and the corresponding Cl will also be provided. The point estimates and Cl for the treatment group differences in proportions will be calculated using Agresti's (2013, page 231) approximation to the Miettinen and Nurminen (1985) method by using pseudo-standard errors.

3.4.2.7 CFBL in Bilateral Percent Ethmoid Cavity Opacification by CT at Week 25/Follow-up 3.4.2.7.1 Part 1

Descriptive summary statistics on the values and changes from baseline to Week 25/Follow-up will be presented.

3.4.2.7.2 Part 2

Mean CFBL in bilateral percent ethmoid cavity opacification by CT at Week 25/Follow-up will be compared between the LYR-220 group and the sham procedure group using an analysis of covariance (ANCOVA) model with fixed-effect terms for treatment group and nasal polyp status with baseline score as a covariate.

LS-means in LYR-220 group and the sham procedure group, and their difference with CIs and p-values will be provided.

Descriptive summary statistics on the values and changes from baseline to Week 25/Follow-up will be presented.

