9.8.1.1.1 Handling of Missing Data and Data Post-Rescue Treatment

Efficacy data collected after early termination will be included in the analysis. A last observation carried forward (LOCF) method will be used to impute post rescue treatment and missing data. Rescue treatments include SCS and/or sinonasal surgery for any reason. There will be no imputation for missing follow-up CT or biomarker assessments.

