# 5 CHANGES FROM PROTOCOL-SPECIFIED STATISTICAL ANALYSES

There is no change from the protocol-specified statistical analyses.

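### The SAP gives four analyses of the SNOT-22 and cardinal-symptom contrast at Weeks 24 and 28 and names none as main, so reported significance can depend on which one is quoted

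*SAP*

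**What the plan says.** SAP 3.4.2.1.2.2 lists four analyses of the Part 2 SNOT-22 change from baseline. The first is "MMRM model without imputation: analysis will be carried out using MMRM model with the CFBL in SNOT-22 score as the dependent variable". The second is headed "MMRM model with subject's worst score imputation", the third "Analysis of covariance (ANCOVA) with multiple imputation" and the fourth "Analysis of covariance (ANCOVA) with last observation carried forward (LOCF) imputation". None is described as main, primary, sensitivity or supportive. SAP 3.4.2.2.2 carries the same methods over to 3CS, the individual symptoms and loss of smell.

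The estimand in SAP 3.4.2.1.1 does not choose between them, because its analysis-model entry describes both the MMRM and the ANCOVA. For rescue it adopts a hypothetical strategy, under which scores after rescue are discarded.

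Protocol 9.8.1.1 specifies an MMRM, and 9.8.1.1.1 adds: "A last observation carried forward (LOCF) method will be used to impute post rescue treatment and missing data". SAP section 5 states: "There is no change from the protocol-specified statistical analyses". SAP 4.2 lists SNOT-22 and 3CS results for an unblinded Primary Lock Analysis intended for a public presentation, without saying which model produces them.

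**The concern.** Followed as written, the SAP yields four p-values for one contrast at Week 24 and gives no rule for which is the result. The protocol cannot break the tie, since its analysis is not on the SAP's list. SAP 3.4 calls this hypothesis testing and protocol 9.8.1.1 sets a 0.05 threshold, so readers will look for a significant or non-significant result. The waiver of multiplicity adjustment (SAP 3.1.7) covers comparisons across endpoints; it says nothing about several tests of one endpoint.

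At stake is how the efficacy findings are read. Any of the four could be presented as pre-specified, first in the Primary Lock presentation and later in the study report, and a reader could not tell whether the choice was made before the data were seen.

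**Working it through.** **Step 1. Set the analyses side by side.**

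| Analysis | Model | After rescue | Other missing data | Visits tested |
|---|---|---|---|---|
| SAP 1 | MMRM | discarded | MAR through the model | all nine |
| SAP 2 | MMRM | subject's worst score | MAR through the model | all nine |
| SAP 3 | ANCOVA | subject's worst score | multiple imputation, 50 datasets | Weeks 24, 28 |
| SAP 4 | ANCOVA | subject's worst score | LOCF | Weeks 24, 28 |
| Protocol | MMRM | LOCF | LOCF | all scheduled |

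Two facts follow. The protocol's analysis differs from every SAP row; SAP 4 shares only LOCF for other missing data. And only SAP 1 matches the hypothetical strategy for rescue, since rows 2 to 4 count rescue as an unfavourable score.

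**Step 2. Significance level.** The SAP gives one-sided tests with two-sided 90% intervals. Both use z(0.95) = 1.645, so they agree at one-sided 0.05, and that level is used below.

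**Step 3. Simulation.** The documents give no SD, effect size, rescue rate or drop-out rate, and the sample size is not power-based, so there is no stated figure to reproduce. From the documents: 20 per arm, Week 24. Assumed: 2,500 trials per scenario, six post-baseline visits instead of nine, rescue triggered by the current score, random drop-out. The MMRM was fitted by EM with unstructured covariance and n - 4 degrees of freedom, as an approximation to REML with Kenward-Roger. Multiple imputation used 50 datasets and no treatment term, as the SAP lists.

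No true effect, proportion significant at one-sided 0.05:

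| Rescue / drop-out | SAP 1 | SAP 2 | SAP 3 | SAP 4 | Any of four | Any of four or protocol |
|---|---|---|---|---|---|---|
| 0% / 0% | 0.048 | 0.048 | 0.048 | 0.048 | 0.052 | 0.052 |
| 10% / 5% | 0.043 | 0.047 | 0.038 | 0.045 | 0.068 | 0.071 |
| 25% / 10% | 0.053 | 0.050 | 0.037 | 0.048 | 0.078 | 0.082 |
| 40% / 14% | 0.065 | 0.048 | 0.033 | 0.050 | 0.093 | 0.098 |

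Relative to nominal, with rescue and drop-out present, the best of four runs from 0.068/0.05 = 1.36 to 0.093/0.05 = 1.86. A second simulation (3,000 trials, SD 18, five post-baseline visits) gave 7.4% at 10% rescue and 10% drop-out, and 8.1% at 20% and 15%.

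Proportion of trials in which the SAP's four disagree on significance:

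| Scenario | d = 0 | d = 0.5 | d = 0.8 |
|---|---|---|---|
| no rescue, no drop-out | 0.7% | 3.6% | 2.6% |
| low | 4.7% | 18.2% | 11.4% |
| middle | 5.6% | 23.8% | 18.7% |
| high | 7.2% | 27.6% | 27.4% |

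With a true effect, realised rescue falls to 8%, 20% and 33% (d = 0.5) and 7%, 18% and 30% (d = 0.8); drop-out is 5%, 10% and 14%.

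**Step 4. Precision.** The Monte Carlo standard error is sqrt(0.05 x 0.95 / 2500) = 0.004 near 5% and sqrt(0.28 x 0.72 / 2500) = 0.009 at 28%. The 0.065 for SAP 1 under heavy rescue lies (0.065 - 0.05)/0.004, nearly four standard errors, above nominal. So the 9.3% is not purely a selection effect; part may come from the approximate degrees of freedom. The independent-test bound, 1 - 0.95^4 = 0.185, does not apply, because the tests are highly correlated (0.84 to 0.92 between SAP 1 and the others in the second simulation).

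**The case against.** The strongest reply is that a lead analysis is already implied. MMRM without imputation is listed first, has its covariance, fallback and degrees-of-freedom rules written out, is the only one that fits the rescue strategy, and appears to be the version reused for CRS-PRO and PGIS, where the SAP says missing data are not imputed. All of that stands and makes the repair easy, but the SAP never says it, and its own analysis-model entry points to two models.

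It is also fair that efficacy is secondary, the trial is not powered, and neither document makes Week 24 decisive. That limits the consequence to the reading of secondary p-values.

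A reader might infer that the trial's error rate is inflated as planned. It is not: running and reporting all four inflates nothing. Inflation needs selective quotation, and the documents do not show that any is intended. A reader might also infer that the four will often conflict. Among null trials with at least one rejection, the share in disagreement is indeed high (for example 0.056/0.078 = 72%), but that is 5.6% of all such trials, and with no rescue or drop-out the analyses nearly coincide.

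Finally, the SAP contents list an Appendix E on changes from the protocol, whose text was not available. If it records the move away from LOCF, section 5 contradicts it; if not, the change is undeclared. Concealment cannot be concluded, and the missing designation remains either way.

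**Conclusion.** The point holds as a gap in pre-specification. At Weeks 24 and 28 the SAP has four undesignated tests of the SNOT-22 and cardinal-symptom contrast, and two at earlier visits; the protocol's analysis is a fifth that section 5 wrongly implies was kept. Significance at Week 24 can depend on the one quoted. Its size is moderate and rests on assumptions: about 7-9% against 5% if only the best is quoted, under assumed rescue of 10-40% and drop-out of 5-15%; about 5% with neither; and disagreement in about 11-28% of trials for effects of 0.5 to 0.8 with rescue and drop-out present. The simulations simplify the SAP's methods, so the decimals are illustrative. The primary safety objective does not change. The correction should be made, but the gap does not invalidate the trial.

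**What to change.** Before the Primary Lock:

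- In SAP 3.4.2.1.2.2, and by reference 3.4.2.2.2, name MMRM without imputation as the main analysis for SNOT-22 and the cardinal symptoms.
- Label the other three as sensitivity or supplementary analyses that carry no separate significance claim.
- Remove ANCOVA from the analysis-model entry of the main estimand in 3.4.2.1.1.
- State in 4.2 that the Primary Lock SNOT-22 and 3CS outputs come from the main analysis.
- Replace the sentence in section 5 with a record that the protocol's LOCF-based MMRM was replaced, and align Appendix E with it.

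This is wording only, and every planned analysis can still be run. The SAP is already signed as version 1.0, so it needs an amendment; under SAP 4.2, a change affecting the analysis after the Primary Lock counts as post hoc. The price is that a favourable supportive analysis cannot stand in for an unfavourable main one. That price may be real: at d = 0.5 with the heaviest assumed rescue, simulated power was 0.33 for MMRM without imputation and 0.45 for ANCOVA with LOCF.

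### Three of the four SNOT-22 and cardinal-symptom analyses score rescued subjects at their worst value, which is not the hypothetical strategy the SAP sets for rescue, and the search for that value does not stop at rescue

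*SAP*

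**What the plan says.** SAP 3.4.2.1.1 defines one estimand for change from baseline in SNOT-22. For rescue the rule is: "ICE1: Rescue treatment: efficacy data collected after rescue treatment will not be used (Hypothetical Strategy"). It outranks the rule for stopping treatment early: "If both ICE1 and ICE2 occur for the same subject, addressing ICE1 takes precedence over ICE2".

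SAP 3.4.2.1.2.2 then lists four Part 2 analyses:

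- **MMRM without imputation.** There is no worst-score rule. "Missing data will be handled by the MMRM under the missing at random (MAR) assumption".
- **MMRM with worst-score imputation.** Here "post-rescue assessments will be imputed with subject's worst score from baseline (including baseline) through Week 28/Follow Up".
- **ANCOVA with multiple imputation.** "Post-rescue Week 24 and Week 28/Follow-up assessments will be imputed with subject's worst score from baseline (including baseline) through Week 28/Follow Up". Multiple imputation is used only for other missing values.
- **ANCOVA with LOCF.** The same worst-score rule applies after rescue, and LOCF is confined to the rest: "Other missing data at Week 24 and Week 28/Follow-up will be imputed with the last value observed before missingness".

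The ANCOVA appears next to the MMRM under the analysis model of the estimand itself. No analysis is called main, sensitivity or supplementary, and no second estimand is defined. SAP 3.4.2.2.2 carries both the estimand and the methods over to cardinal symptoms and loss of smell. CRS-PRO and PGIS (SAP 3.4.2.3 and 3.4.2.4) use only the MMRM with no imputation and are not affected.

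**The concern.** A hypothetical strategy asks what the score would have been had rescue not occurred. Giving a rescued subject the worst score on record instead counts rescue as a bad outcome. The resulting difference mixes the effect on symptoms with the difference in rescue rates.

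The search window is a second, smaller problem. It runs through Week 28 whatever the date of rescue. Subjects rescued with steroids stay in follow-up (SAP 3.6.6), so post-rescue scores will exist, and the highest of them can become the analysed value although ICE1 excludes it. The Primary Lock Analysis (SAP 4.2) takes place once all subjects have completed Week 24, when some Week 28 scores may be outstanding. A rescued subject's imputed Week 24 value could therefore change between that lock and the final one.

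SNOT-22 total and 3CS are the efficacy results selected for the Primary Lock Analysis, and SAP 4.2 does not say which of the four analyses supplies them. A reader could receive estimates of two different quantities under one estimand.

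**Working it through.** The documents state no SD, effect size or rescue rate, so there is no figure of theirs to reproduce. The inconsistency rests on the text. The sizes below rest on assumed inputs.

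**Count.** One of the four analyses has no worst-score rule and three have it.

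**One subject (invented scores).** Baseline is 60. Scores at Weeks 2, 4, 6 and 8 are 50, 46, 45 and 48. Rescue follows Week 8. Scores at Weeks 12, 16, 20, 24 and 28 are 40, 66, 45, 42 and 44.

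- ICE1 as written: the values from Week 12 on are not used.
- Worst score up to rescue: max(60, 50, 46, 45, 48) = 60, a change of 0.
- Worst score through Week 28: max(60, ..., 66, ...) = 66, a change of +6. The analysed Week 24 value is then the Week 16 score, observed after rescue.

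**Effect of the rule, by hand.** Assume a no-rescue change of −25 on LYR-220 and −15 on sham, and let the worst score equal baseline (change 0). With rescue proportions r_T and r_S:

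difference = −25(1 − r_T) + 15(1 − r_S), and shift from −10 = 25 r_T − 15 r_S.

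**Effect of the rule, by simulation.** There were 200,000 subjects per arm, with baseline mean 50 and SD 15, between-subject SD 10 and visit SD 8. The mean changes were as above, reached by Week 12. Rescue was independent of outcome, with the first post-rescue visit between Weeks 4 and 20. Scores were truncated to 0–110, which makes the no-rescue difference −9.30 to −9.41. Each range covers two cases: rescue lowers later scores by 10 points, or has no effect.

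| Rescue, LYR-220 / sham | Hand: difference (shift) | Simulated worst-score difference, window to Week 28 | Simulated shift |
|---|---|---|---|
| 5% / 10% | −10.25 (−0.25) | −9.93 to −10.05 | −0.6 to −0.7 |
| 10% / 10% | −9.00 (+1.00) | −8.50 to −8.61 | +0.7 to +0.8 |
| 5% / 25% | −12.50 (−2.50) | −13.06 to −13.19 | −3.7 to −3.8 |
| 10% / 40% | −13.50 (−3.50) | −14.60 to −15.00 | −5.3 to −5.6 |
| 25% / 10% | −5.25 (+4.75) | −4.29 to −4.30 | +5.0 |

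A separate calculation assumed a no-rescue change of −10 and within-subject SD 8 to 12. The mean worst-score change was +4.6 to +10.5, a gap of 14.6 to 20.5 points per rescued subject. For a 15-point difference in rescue rates (3 subjects in an arm of 20) the shift is 0.15 × 14.6 = 2.2 to 0.15 × 20.5 = 3.1.

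**Effect of the window alone.** In the first simulation the largest change from ending the search at rescue was 15.00 − 14.72 = 0.28 points. In the second calculation, stopping at rescue lowers the imputed value by 1.5 (4.6 − 3.1) to 3.1 (10.5 − 7.4) points, so the contribution is 0.15 × 1.5 = 0.2 to 0.15 × 3.1 = 0.5.

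**The case against.** The sponsor can say that running several analyses with different rules for rescue is sound practice, that each rule is stated openly, and that the first MMRM matches ICE1. Efficacy is secondary (SAP 3.4.1), and the sample size is not based on power (SAP 2.2.5). All of this is true and limits the severity. It does not remove the mismatch, because the SAP never calls the worst-score analyses supplementary and puts the ANCOVA inside the estimand.

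On the window, SAP 3.1.10.3.2 refers intercurrent events to the estimand section. One could therefore apply ICE1 first and search only the pre-rescue scores that remain. That reading is possible, but the SAP does not state it, and the text of the rule points the other way. Subjects who have rescue surgery during treatment leave the study (SAP 3.6.7), so the question mainly concerns steroid rescue.

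A reader might infer that post-rescue scores will routinely re-enter. The documents do not support that, since such a score enters only when it is the subject's highest. In the first simulation this happened in 1–2% of rescued subjects when rescue lowered scores by 10 points, and in 5–15% when it had no effect. Shares of 29–36% arise in a noisier model with independent visit errors and no effect of rescue on symptoms. With a 10-point rescue effect the same model gives 5–13%.

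A reader might also infer that the rule favours LYR-220. It need not: with equal rescue rates the difference shrinks in the table, and with more rescue on LYR-220 it falls by about 5 points.

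**Conclusion.** The point stands as an inconsistency in the SAP. One hypothetical estimand is paired with three analyses that follow a composite-type rule, and that rule's search window can reuse data the estimand excludes.

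Under the assumptions shown, the worst-score rule moves the SNOT-22 difference by roughly 2 to 5 points (5.6 in the most extreme case tried) when rescue rates differ by about 15 to 30 percentage points. The direction depends on which arm has more rescue. The shift is about 1 point or less when the rates are equal or 5 points apart. The window accounts for about 0 to 0.5 points. For scale, the SAP's minimal clinically important difference is 9.

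The first simulation gives rescued subjects the average no-rescue course. If those rescued would have done badly anyway, the shifts would probably be smaller. No size was worked out for the cardinal symptoms. The textual finding is firm and the sizes are illustrative. The SAP should be corrected, but the safety objective of the trial is not touched.

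**What to change.** 1. Name the MMRM without imputation as the main analysis of the hypothetical estimand, and state that post-rescue values are set to missing in it.
2. Label the worst-score MMRM and both ANCOVAs as supplementary, with their own composite-strategy estimand. Do the same for cardinal symptoms and loss of smell.
3. Restrict the worst-score search to values from baseline up to the date of rescue.

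I would not replace the worst-score rule with MAR imputation in the multiple-imputation ANCOVA. That would largely repeat the first MMRM and remove a check on the MAR assumption for rescued subjects.

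In the same edit, reconcile protocol 9.8.1.1.1, which uses LOCF for post-rescue data. None of the four SAP analyses does so, yet SAP Section 5 declares no change from the protocol.

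The cost is SAP wording and a minor programming change, with no new data. The worst-score values become slightly less pessimistic. Under SAP 4.2, any such change made after the Primary Lock Analysis has to be reported as post hoc.
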